# Clinical Study Protocol

## Johnson & Johnson Vision Care, Inc.

### Biomicroscopy (Slit Lamp Findings)

Slit lamp findings (SLF) are converted to a binary response as  $Y = 1$  if a subject eye has a clinically significant SLF and  $Y = 0$  otherwise for analysis purpose. From the historical data there was no or extremely low rate for clinically significant SLF for the study lenses. Assuming no difference between study lenses and a correlation of 0.70 between left and right eyes within the same subject, a total of 2000 replicating trials were simulated with clinically significant SLF rate of 2% (worse-case scenario). Given the rare event binary outcome of slit lamp findings, each replicated sample was analyzed using a Bayesian beta-binomial model with correlated binary data (Diniza et al; 2010). Sample size was estimated to achieve a minimal statistical power of 80% with a non-inferiority margin of 5% (Test – Control) based on the simulated data. For each simulated trial, the lower bound of the 95% central posterior credible interval constructed for the percentage difference was compared to the 5% margin. With the proposed sample size, there was at least 80% of the estimated 95% credible intervals with upper bound being below 5%.

### CLUE Overall Comfort

Power for CLUE overall comfort was estimated using a two independent sample  $t$  test in PROC Power assuming the Test lens is 2 points higher than the Control lens and a common standard deviation of 23. A non-inferiority margin of -5 points was used since this is considered to be no more than a 10% shift in the population distribution of CLUE scores.

### CLUE Overall Handling

Power for CLUE overall handling was estimated using PROC Power for a two independent sample  $t$  test assuming the Test lens is 2 points lower than the Control lens and a common standard deviation of 21. A non-inferiority margin of -5 points was used since this is considered to be no more than a 10% shift in the population distribution of CLUE scores.

### Clarity of Vision Indoors in Bright Light

Clarity of vision indoors in bright light will be evaluated at 2-week follow-up using a 5-point Likert scale (1: Excellent, 2: Very Good, 3: Good, 4: Fair and 5: Poor) with a “Not Applicable” response option. Responses to clarity of vision indoors in bright light will be converted into a binary variable for the purpose of analysis (Excellent = 1 and others = 0) and “Not Applicable” will not be included in the analysis. Based on historical data from [REDACTED] and [REDACTED] (Interim), it was assumed the percentage of subjects with an “Excellent” rating was 60% and 50% for the Test and Control lenses, respectively. Power was calculated using PROC POWER for Pearson chi-square test for two proportions. The non-inferiority odds ratio margin of 0.67 was used, which corresponds to no more than a 10% difference between the Test and Control lenses.

### Overall Preference While Using Computer Screens & Digital Devices

Responses to overall preference while using computer screens & digital devices in the Test lens group will be collapsed into three categories for the purpose of analysis (Prefer Test Lens, No Preference, and Prefer Habitual Lens). Based on historical data from [REDACTED] and [REDACTED]

# Clinical Study Protocol

## Johnson & Johnson Vision Care, Inc.

█ (Interim) for period 1, it was assumed that the percentage of subjects preferring Test lens was 0.4, the percentage of subjects preferring Habitual lens was 0.2, and the percentage of subjects with no preference was 0.4. A total of 2000 replicating trials were simulated. To estimate statistical power, the simulated multinomial data were analyzed using a generalized linear regression model with a generalized logit link function and tested for statistical superiority (preference ratio of preferring Test to Habitual).

Table 11 below summarizes the required number of completed subjects to achieve a minimum of 80% statistical power for the primary endpoints. Table 12 shows the statistical power for the secondary endpoints based on the sample size determined by the primary endpoints.

Table 11: Sample Size Estimation for the Primary Endpoints

Endpoint	Hypothesis Testing	Sample Size	Power
Monocular Distance LogMAR VA	Non-inferiority	16	84%
CLUE Vision	Non-inferiority	286	80%
Lens Fit Acceptance	Non-inferiority	140	83%
Slit Lamp Findings	Non-inferiority	240	83%

Table 12: Power Estimation for the Secondary Endpoints

Endpoint	Hypothesis Testing	Sample Size	Power
CLUE Comfort	Non-inferiority	286	73%
CLUE Handling	Non-inferiority	286	23%
Situational Visual Performance – Indoor (Clarity of Vision Indoors in Bright Light)	Non-inferiority	286	93%
Situational Visual Performance – Digital Devices (Overall Preference While Using Computer Screens & Digital Devices)	Superiority	143 for Test Lens Group	88%

As indicated in Table 11 above, the sample size chosen for this study was primarily driven by the primary endpoint of CLUE overall quality of vision in order to achieve a statistical power of at least 80% for all primary endpoints. The plan is to enroll approximately 320 eligible subjects with a target of 286 to complete the study (143 per arm).

### 14.3. Analysis Populations

#### **Safety Population:**

All subjects who are administered any test article excluding subjects who drop out prior to administering any test article. At least one observation should be recorded.

# Clinical Study Protocol

## Johnson & Johnson Vision Care, Inc.

### **Per-Protocol Population:**

All subjects who successfully complete all visits and do not substantially deviate from the protocol as determined by the trial cohort review committee prior to database hard lock. Justification for the exclusion of subjects with protocol deviations from the per-protocol population set will be documented in a memo to file.

### **Intent-to-Treat (ITT) Population:**

All randomized subjects regardless of actual treatment and subsequent withdrawal from the study or deviation from the protocol. At least one observation should be recorded.

#### **14.4. Level of Statistical Significance**

All planned analysis for this study will be conducted with an overall type I error rate of 5%.

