### **2.3. Hypotheses**

All the following primary hypotheses must be met for the objectives of this study to be satisfied:

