# **Clinical Study Protocol**

## **Johnson & Johnson Vision Care, Inc.**

### Secondary Hypotheses

#### Efficacy

1. The JJVCI investigational contact lens is non-inferior to the control lens with respect to overall CLUE handling score at the follow-up visit. A non-inferiority margin of -5 points on the CLUE scale will be used.
2. The JJVCI investigational contact lens is non-inferior to the control lens with respect to overall CLUE comfort score at the follow-up visit. A non-inferiority margin of -5 points on the CLUE scale will be used.
3. The JJVCI Investigational contact lens will be non-inferior to the Control lens with respect to the proportion of subjects with Excellent responses to the statement “Clarity of Vision indoors in bright light (████████)” at the follow-up visit. A non-inferiority margin of 0.67 for odds ratio will be used.
4. The JJVCI Investigational contact lens will be superior to the Control habitual lens with respect to overall preference while using computer screens & digital devices at the follow up visit.

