### **14.2. Sample Size Justification**

This study is designed and powered to demonstrate non-inferiority of the Test lens compared to the Control lens with respect to the primary endpoints: slit lamp findings, fit acceptance, distance monocular logMAR VA, and CLUE overall quality of vision. Sample size was estimated to achieve a minimum statistical power of 80% for logMAR VA and CLUE vision with a 2-sided type I error of 0.05 each, and a minimum statistical power of 80% for slit lamp findings and lens fit acceptance with the 95% central posterior credible interval. For information purpose, power was estimated for the secondary endpoints using the sample size determined by the primary endpoints.

Sample size/power estimation was based on historical hard-lock data from [REDACTED] and [REDACTED] [REDACTED] and the interim read data from [REDACTED]. The same type of Test and Control lenses were investigated in [REDACTED] and [REDACTED] with a 2×2 crossover design. Test lenses in [REDACTED] were made from the pilot line while Test lenses in [REDACTED] and the current study are produced from the manufacturing line. [REDACTED] is a 6×6 crossover study with 6 different types of lenses.

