##### Hypothesis Testing

The null and alternative hypotheses for testing non-inferiority of the Test lens relative to the Control lens with respect to CLUE vision scores are as follows:

$$H_0: \mu_T - \mu_C \leq -5$$
$$H_A: \mu_T - \mu_C > -5$$

Where,  $\mu_T$  represents the mean CLUE vision score for the Test lens and  $\mu_C$  represents the mean CLUE vision score for the Control lens. Non-inferiority will be declared if the lower bound of the 2-sided 95% confidence interval of the difference (Test – Control) is greater than -5. If non-inferiority of the Test lens over Control lens is met, then superiority will be assessed. If the lower bound is greater than 0, then superiority of the Test lens over the Control lens will be established.

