### Hypothesis Testing

The null and alternative hypotheses for testing non-inferiority of the Test lens relative to the Control lens with respect to logMAR visual acuity are as follows:

$$H_0: \mu_T - \mu_C \geq 0.05$$
$$H_A: \mu_T - \mu_C < 0.05$$

Where,  $\mu_T$  represents the mean logMAR VA score for the Test lens and  $\mu_C$  represents the mean logMAR VA score for the Control lens. Non-inferiority will be declared if the upper bound of the 2-sided 95% confidence interval of the difference (Test – Control) is less than 0.05. If non-inferiority of the Test lens over Control lens is met, then superiority will be assessed. If the upper bound is less than 0, then superiority of the Test lens over the Control lens will be established.

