##### CLUE Overall Comfort and Overall Handling

CLUE overall comfort and handling will be analyzed using the same statistical method described for CLUE overall quality of vision.

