# Clinical Study Protocol

## Johnson & Johnson Vision Care, Inc.

2-sided 95% confidence interval is above 0.67. If non-inferiority of the Test lens over Control lens is met, then superiority will be assessed. If the lower bound is above 1.0, then superiority of the Test lens over the Control lens can be concluded.

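### Section 14.4 states an overall 5% type I error, but three separate superiority claims over Control have no order or adjustment, so 5% is not guaranteed for them

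*Combined protocol and SAP*

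**What the plan says.** Section 14.4 consists of one sentence: "All planned analysis for this study will be conducted with an overall type I error rate of 5" percent. It gives no method and does not say whether the 5% is one- or two-sided. Section 14.2 sizes the study "for logMAR VA and CLUE vision with a 2-sided type I error of 0.05 each".

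For the primary non-inferiority tests, section 2.3 states: "All the following primary hypotheses must be met for the objectives of this study to be satisfied".

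Superiority over Control is then provided for on three endpoints, each time after non-inferiority on that same endpoint:

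- CLUE vision (section 14.5): "If the lower bound is greater than 0, then superiority of the Test lens over the Control lens will be established".
- LogMAR visual acuity (section 14.5): "If the upper bound is less than 0, then superiority of the Test lens over the Control lens will be established".
- Indoor clarity, on the odds-ratio scale (section 14.6): "If the lower bound is above 1.0, then superiority of the Test lens over the Control lens can be concluded".

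For CLUE comfort and handling, section 14.6 says only that they "will be analyzed using the same statistical method described for CLUE overall quality of vision". The secondary hypotheses in section 2.3 claim non-inferiority only, for example "The JJVCI investigational contact lens is non-inferior to the control lens with respect to overall CLUE handling score at the follow-up visit".

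On covariates, section 5.1 stratifies randomisation by site and habitual lens type. Site is a random effect in every efficacy model in sections 14.5 and 14.6. Habitual lens type is optional in all of them, and no criterion is given for including it.

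**The concern.** An overall 5% for everything planned and 5% for each endpoint are different promises. The rule that all primary hypotheses must hold protects the primary non-inferiority conclusion without adjustment. It is not written as a gate for superiority, and a superiority claim on any one of three endpoints is an any-of-several claim.

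The gate that is written, non-inferiority on the same endpoint, stops no false superiority claim: an interval that lies wholly above 0 (or above an odds ratio of 1) also lies above the margin.

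What is at stake is a follow-on statement that the Test lens is superior to Control on a named endpoint. A reader of the protocol would take it as covered by the stated 5%.

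The optional stratum is a separate and smaller matter. It leaves the final model undefined in the protocol and may give up a little precision.

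**Working it through.** **1. Reproduce the plan's figures.** Inputs from section 14.2: 143 completers per arm; CLUE vision difference +2, SD 21, margin -5; indoor clarity 60% v 50%, margin 0.67.

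- CLUE vision: SE = 21 × √(2/143) = 2.484. The distance from the margin is 2 + 5 = 7 points. The noncentral t at one-sided 2.5% gives power 80.2% (Table 11: 80%). One-sided 5% would give 87.8%, so the plan used 2-sided 0.05.
- Indoor clarity: log odds ratio ln(1.5) = 0.405; SE = √(1/(143 × 0.24) + 1/(143 × 0.25)) = 0.239; Φ((0.405 + 0.400)/0.239 - 1.96) = 92.1% (Table 12: 93%).

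The 2-sided 95% interval therefore puts 2.5% in the direction that favours Test for each superiority claim.

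**2. Chance of at least one false superiority claim, lenses equal on every endpoint.** If independent: 1 - 0.975^k. With a common correlation r between the test statistics: 1 - ∫ φ(u) Φ((1.96 - √r·u)/√(1 - r))^k du. Bound under any dependence: k × 2.5%. The documents give no correlations, so r is an assumption.

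| Claims counted | r = 0 | r = 0.5 | r = 0.7 | r = 0.9 | Bound |
|---|---|---|---|---|---|
| Two primary (CLUE vision, logMAR) | 4.94% | 4.54% | 4.17% | 3.52% | 5.0% |
| Three written claims | 7.31% | 6.27% | 5.46% | 4.18% | 7.5% |

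With three claims the total exceeds 5% when r is below about 0.785. If the 5% is two-sided, so that 2.5% is allowed in the favourable direction, every entry exceeds it.

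**3. On the plan's planning assumptions.** CLUE vision (+2) and indoor clarity (60% v 50%) are assumed truly better with Test, so superiority claims there would be true. Only logMAR is assumed equal, which leaves a false-claim chance of 2.5%.

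**4. Stratum, CLUE vision model.** Let habitual lens type explain a share R² of the variance left after the other terms (an assumption; the documents give none), balanced within strata. The true SE is 2.484 × √(1 - R²). With the term omitted, power = P(Z > (1.96 × 2.484 - 7)/true SE). With it included, power = P(Z > 1.96 - 7/true SE).

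| R² | Omitted | Included | One-sided error if omitted |
|---|---|---|---|
| 1% | 80.6% | 80.9% | 2.44% |
| 5% | 81.1% | 82.4% | 2.22% |

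The error with the term omitted is below the nominal 2.5%, so intervals are slightly too wide, not too narrow. This calculation covers the linear CLUE vision model only.

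**The case against.** **Superiority over Control is incidental.** It is in no objective or hypothesis and in no row of Tables 11 and 12; the one superiority row there, digital devices, compares Test with the habitual lens. That is true and limits the importance of the point. But sections 14.5 and 14.6 let the claim be established or concluded in a trial labelled confirmatory, and section 14.4 covers all planned analysis.

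**The two primary superiority claims already meet a literal 5%.** This stands: 4.94% if independent, 5.0% at most. The excess comes only from the secondary claim and is at most 2.5 points.

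**The primary tests act as a gate.** No such gate is written. If CLUE vision non-inferiority were required first, simulation with equal lenses gives 4.9%, 5.9% and 4.2% at correlations 0, 0.5 and 0.9, so 5% would still not be guaranteed.

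**The SAP may settle it.** Section 14.1 announces a stand-alone SAP to be finalised before database lock, which could add an order or a covariate rule. Its text is not available here, and the 5% statement is made in the protocol.

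**A reader might count five claims.** If comfort and handling inherit the superiority step, the figures are 11.89% if independent and 5.08% at 0.9. Shared method wording is thin support when section 2.3 states only non-inferiority for both, so five is not the main count.

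**On the stratum,** the baseline CLUE score is always in the CLUE models and is answered about the habitual lenses, so it may already absorb much of this effect. The digital-device analysis uses the Test group only, so stratified randomisation gives no reason to require the term there. Both points stand.

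**Conclusion.** The point holds as a mismatch between a stated property and the written rules. With equal lenses, the chance of a false superiority claim over Control is between 4.2% and 7.3% for assumed correlations from 0.9 to 0, with a ceiling of 7.5%. It rests on counting the three claims the protocol writes out and, for the correlated figures, on a common correlation the documents do not supply.

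Three stronger readings are not supported:

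- **The trial's main conclusion is inflated.** It is not: all four primary hypotheses must hold, and section 2.1 requires all the market preferences together for the secondary objective. The step from non-inferiority to superiority within one endpoint is also sound.
- **5% is always exceeded.** It is not: high correlation, or the plan's own assumptions, keep the error below it.
- **Leaving out the stratum produces false claims.** It works the other way; the issue is clarity and a small gain in precision.

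**What to change.** **In section 14.4, choose one:**

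- (a) Limit the 5% statement to the primary non-inferiority decision and label superiority over Control as descriptive. Cost: no superiority claim over Control is confirmatory.
- (b) After all four primary tests succeed, test superiority in a stated fixed sequence, or by Holm at one-sided 2.5% overall. For three claims the Holm thresholds are 2.5%/3 = 0.83%, 2.5%/2 = 1.25% and 2.5%, so no claim rests on an interval looser than the 2-sided 95% interval. Cost, on the plan's assumptions: at the first Holm threshold, superiority power falls from 39.6% to 24.3% for indoor clarity and from 12.4% to 5.6% for CLUE vision. These are lower bounds, because Holm relaxes after each rejection. A fixed sequence costs the first endpoint nothing.

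Under either option, state whether comfort and handling carry a superiority step.

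**Separately, in sections 14.5 and 14.6,** always include habitual lens type in the CLUE and logMAR models. Include it in the indoor-clarity model too, noting that the odds ratio then becomes conditional on the stratum, whereas section 14.2 relates the 0.67 margin to a difference of about 10% between the lenses. Do not require it on this ground in the digital-device model. Cost: one parameter per model.

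Neither change affects sample size, visits or the rule for the primary decision.

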#### **14.5. Primary Analyses**

##### **Primary Efficacy Analyses:**

Primary efficacy analyses will be conducted on the Per-Protocol (PP) population. Sensitivity analysis may be considered on the Intent-to-Treat (ITT) population with no missing data imputation.

##### CLUE Overall Quality of Vision

CLUE vision scores will be analyzed using a linear mixed model to compare the Test and Control lenses at the 2-week follow-up evaluation. The model will include baseline CLUE vision score and lens type as fixed effects and clinical site as a random effect (G-side). Other subject characteristics such as age, gender, iris category (dark iris and light iris), and habitual lens type (habitual daily disposable and habitual daily wear reusable) will be included when appropriate. The Kenward and Roger method will be used for the denominator degree of freedom.

##### Hypothesis Testing

The null and alternative hypotheses for testing non-inferiority of the Test lens relative to the Control lens with respect to CLUE vision scores are as follows:

$$H_0: \mu_T - \mu_C \leq -5$$
$$H_A: \mu_T - \mu_C > -5$$

Where,  $\mu_T$  represents the mean CLUE vision score for the Test lens and  $\mu_C$  represents the mean CLUE vision score for the Control lens. Non-inferiority will be declared if the lower bound of the 2-sided 95% confidence interval of the difference (Test – Control) is greater than -5. If non-inferiority of the Test lens over Control lens is met, then superiority will be assessed. If the lower bound is greater than 0, then superiority of the Test lens over the Control lens will be established.

##### Monocular Distance logMAR Visual Acuity

# Clinical Study Protocol

## Johnson & Johnson Vision Care, Inc.

Monocular distance logMAR VA under bright HLHC will be analyzed using a linear mixed model. The model will include lens type as a fixed effect. Other subject characteristics such as age, gender, iris category, and habitual lens type will be included when appropriate. Site will be included in the model as a random effect (G-side). The covariance of residuals between measurements within the same subject across eyes (R-side random effect) will be modeled using Unstructured (UN) covariance structure. If the model does not converge, then compound Symmetry (CS) covariance structure will be considered. The Kenward and Roger method will be used for the denominator degree of freedom.

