### Primary Efficacy Endpoints:

#### Distance Monocular LogMAR Visual Acuity (VA)

Distance monocular logMAR VA will be assessed for each subject eye at the two-week follow-up evaluation using ETDRS charts at 4 meters under high luminance high contrast (HLHC) condition.

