# **Clinical Study Protocol**

## **Johnson & Johnson Vision Care, Inc.**

stratified by site and type of habitual lens wear (daily disposable and daily wear reusable). The ratio of habitual wearers of daily disposable lenses to habitual wearers of daily wear reusable lenses is 7:3 within each study site (7 habitual wearers of daily disposable lenses versus 3 habitual wearers of daily wear reusable lenses). See Table 1. The random scheme will be generated using the PROC PLAN procedure from Statistical Analysis System (SAS) Software Version 9.4 or higher (SAS Institute, Cary, NC).

Randomization will be performed at visit 1. The following must have occurred prior to randomization:

- Informed consent must have been obtained.
- The subject must have met all eligibility criteria.
- The subject's screening and baseline information must have been collected.

When dispensing test articles, the following steps should be followed to maintain randomization codes:

1. Investigator or designee (documented on the Delegation Log) will consult the lens fitting schedule to obtain the test article assignment for that subject prior to dispensing.
2. Investigator or designee will record the subject's number on the appropriate line of the lens fitting schedule.
3. Investigator or designee will pull the appropriate test articles from the study supply. All test articles that are opened, whether dispensed (placed/fit on eye or dispensed outside the clinical site) or not, must be recorded on the Test Article Accountability Log in the "Dispensed" section.

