**Clinical Study Protocol**  
**Johnson & Johnson Vision Care, Inc.**

Visit 1: Screening			
Step	Procedure	Details	
1.5	Habitual Wear Time	Record the average wearing time and comfortable wearing time.	
1.6	SCL Rx Confirmation	
The investigator confirms:
 
 
1. The subject is wearing a SCL Rx that has been confirmed current (up-to-date) within the prior 6 months.
 
2. The subject has worn the up-to-date SCL Rx for at least 2 weeks.
 
	
1.7	Eligibility after Screening	
All responses to Screening Inclusion Criteria questions must be answered “yes” and all responses to Exclusion Criteria must be answered “no” for the subject to be considered eligible.
 
If subject is deemed to be ineligible after screening, proceed to Final Evaluation and complete Subject Disposition. Refraction and Biomicroscopy forms do not need to be completed as part of Final Evaluation.
	

Visit 1: Baseline			
Step	Procedure	Details	
1.8	Baseline Questionnaire	
The subject will respond to the following Baseline Questionnaires based on their habitual lenses:
 
 
1. CLUE Baseline
 
	
1.9	Entrance Visual Acuity	Record the distance Snellen visual acuity (OD, OS, and OU) to the nearest letter with their habitual contact lens correction in place. Subjects must read the smallest line until at least 50% of the letters are read incorrectly.	
1.10	Remove Habitual Lens	The subject’s habitual lenses will be removed and stored in their own lens case. If they forgot to bring their lens case, one will be provided to them.	

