**Clinical Study Protocol**  
**Johnson & Johnson Vision Care, Inc.**

Visit 1: Baseline		
Step	Procedure	Details
1.11	Slit Lamp Biomicroscopy	
FDA Slit Lamp Classification Scale will be used to grade the findings and determine eligibility.
 
If any of these slit lamp findings are grade 3 or higher (FDA scale), the subject may not continue at this time, but may return up to one additional time to determine eligibility. If discontinued a final examination must be completed.
 
Limbal and Bulbar Conjunctival Hyperemia findings (████████) and Corneal Staining Assessment (████████) will also be collected for internal purposes.
 
If the clearance of the fluorescein needs to be expedited, preservative-free rewetting drops or saline may be instilled.

1.12	Keratometry	Record the keratometry readings OD and OS in diopters. This can come from any appropriate instrument so long as the same instrument is used at the Final Evaluation.
1.13	Iris Color	The investigator will record the subject's iris color based on the scale provided.
1.14	Subjective Spherocylindrical Refraction	Complete subjective spherocylindrical refraction and record the resultant distance visual acuity (OD, OS, and OU) to the nearest letter.
1.15	Eligibility after Baseline	
All responses to Inclusion Criteria questions must be answered "yes" and all responses to Exclusion Criteria questions must be answered "no" for the subject to be considered eligible.
 
If subject is deemed to be ineligible after baseline, proceed to Final Evaluation and complete Subject Disposition. Refraction and Biomicroscopy forms do not need to be completed as part of Final Evaluation.

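### The logMAR acuity model does not prespecify baseline acuity, though each eye's acuity is recorded before randomisation; this loses some precision and leaves the non-inferiority result unaffected

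*Combined protocol and SAP*

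**What the plan says.** Section 14.5 (Monocular Distance logMAR Visual Acuity) sets out a linear mixed model with random site and an unstructured residual covariance across a subject's two eyes. On fixed effects it says: "The model will include lens type as a fixed effect. Other subject characteristics such as age, gender, iris category, and habitual lens type" are to be added when judged suitable. Baseline acuity is not in the list, and the list is open-ended.

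For the other primary efficacy endpoint, the same section carries a similar open list but names the baseline separately: "The model will include baseline CLUE vision score and lens type as fixed effects".

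Two acuity measurements precede randomisation in Section 7.2. Step 1.9: "Record the distance Snellen visual acuity (OD, OS, and OU) to the nearest letter with their habitual contact lens correction in place". Step 1.14: "Complete subjective spherocylindrical refraction and record the resultant distance visual acuity (OD, OS, and OU) to the nearest letter". The study lens is assigned at step 1.16, and Section 5.1 makes it a precondition of randomisation that "The subject's screening and baseline information must have been collected".

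The outcome itself is measured once, per Section 2.2: "Distance monocular logMAR VA will be assessed for each subject eye at the two-week follow-up evaluation using ETDRS charts at 4 meters". Once non-inferiority at 0.05 logMAR is met, the logMAR hypothesis-testing text moves on to superiority: "If the upper bound is less than 0, then superiority of the Test lens over the Control lens will be established".

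**The concern.** A pre-randomisation measurement that predicts the outcome removes residual variance when it is a model term. Here the data already exist per eye, and the sponsor adjusts for baseline in the sister model without explaining why acuity is handled differently.

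High non-inferiority power does not fully settle the matter, because the plan also allows a superiority conclusion on acuity. That test, and the width of the reported interval, depend directly on the residual variance. Leaving the covariate to discretion also means that a primary model term would be chosen later, with no stated rule.

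**Working it through.** **Inputs from the documents**
- Residual covariance matrix (Section 14.2): variances 0.002492 and 0.000736, covariance 0.000689.
- Margin 0.05 logMAR, assumed true difference 0, two-sided 0.05 (Sections 2.3 and 14.2).
- Completers: 286, 143 per arm. Table 11 gives N = 16 and 84% power for logMAR.

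**Assumptions not in the documents**
- r, the baseline-to-follow-up correlation: 0.3 and 0.5, with 0 for the plan as written.
- A true gain of 0.010 logMAR for superiority (half a letter, at 0.02 logMAR per letter).
- Adjustment multiplies the residual variance by (1 - r^2). Site variance is ignored.

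**1. Reproduce Table 11.** Variance of the simple two-eye mean: (0.002492 + 0.000736 + 2 × 0.000689)/4 = 0.0011515. At N = 16, SE = sqrt(4 × 0.0011515/16) = 0.01697. Power = Φ(0.05/0.01697 - 1.96) = Φ(0.99) = 83.8%, against 84% stated. This match uses a normal approximation. Section 14.2 describes an F test, which with 14 degrees of freedom gives 78.2% for this variance.

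**2. Variance implied by the planned model.** With an unstructured covariance and no eye effect named, the lens contrast weights the two eyes by generalised least squares (GLS):

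(0.002492 × 0.000736 - 0.000689^2)/(0.002492 + 0.000736 - 2 × 0.000689) = 0.000735.

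At N = 16 with 14 degrees of freedom this gives 92.9%. Both variances are carried forward because the two-eye mean comes closer to the plan's figure, while GLS is closer to the planned model.

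**3. Non-inferiority at N = 286.** With the larger variance, SE = sqrt(4 × 0.0011515/286) = 0.00401. The margin is 0.05/0.00401 = 12.5 standard errors away, so power is about 100% for either variance and any r.

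**4. Precision and superiority at N = 286.** SE(r) = sqrt(4v(1 - r^2)/286). Power uses the noncentral t distribution with 283 degrees of freedom.

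| r | Narrowing, 1 - sqrt(1 - r^2) | Half-width, two-eye mean | Half-width, GLS | Power at 0.010, two-eye mean | Power at 0.010, GLS |
|---|---|---|---|---|---|
| 0 | none | 0.0079 | 0.0063 | 70% | 88% |
| 0.3 | 5% | 0.0075 | 0.0060 | 74% | 90% |
| 0.5 | 13% | 0.0068 | 0.0055 | 82% | 95% |

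The narrowing does not depend on which variance is used. In completers, 286/(1 - r^2) gives 314 at r = 0.3 and 381 at r = 0.5.

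**5. Sensitivity to the assumed gain.** At 0.005 logMAR, power at r = 0 and r = 0.5 is 24% and 30% with the two-eye mean, and 34% and 43% with GLS. At 0.015 the unadjusted two-eye-mean power is already Φ(0.015/0.00401 - 1.96) = 96%. The power gain therefore matters only over a narrow band of small true differences.

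**The case against.** The strongest reply is that superiority on acuity is not a design goal. Section 2.3 hypothesises non-inferiority only, Section 14.2 powers for non-inferiority, and it assumes equal lenses. Under that assumption there is no superiority power to lose. This stands, and it is why the point is minor. The plan does nevertheless permit the superiority claim and sets no minimum size for it.

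The comparison with CLUE is also not like for like. CLUE uses the same questionnaire at baseline, whereas ETDRS logMAR is scheduled only at Visit 2. Step 1.9 is Snellen acuity; step 1.14 names no chart and is taken through full spherocylindrical correction. The outcome is acuity through a spherical lens, with up to 1.00 D of cylinder allowed, and entry requires 20/25 or better in each eye. All of this may lower r. It does not bias a randomised comparison, because a baseline covariate need not share the outcome's scale.

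Finally, the covariate list is open, and Section 14.1 defers detail to a stand-alone SAP that is not in the file. Baseline acuity is unnamed, not excluded. But an open list with no selection rule is not prespecification.

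Three stronger readings are not supported. A reader might infer that the omission biases the lens comparison or threatens the primary conclusion; it does neither. A reader might take 70% as the plan's superiority power; that depends on the assumed 0.010 gain and on the simple two-eye mean, and the planned covariance structure points nearer 88%. A reader might also suppose that the sponsor considered baseline acuity and rejected it; no section says so.

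**Conclusion.** The point holds as a minor efficiency gain. Baseline acuity is not prespecified in the logMAR model, it is available per eye before randomisation, and adding it would narrow the interval by about 5% to 13% for r between 0.3 and 0.5. For an assumed 0.010 logMAR gain, superiority power would rise from about 88% to 90-95% (GLS) or from about 70% to 74-82% (two-eye mean).

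The direction is secure for any non-trivial r, since one degree of freedom costs almost nothing at 286 completers. The size is not secure: neither r nor the 0.010 gain is in the documents. The covariance matrix comes from earlier data, and Table 9 labels the earlier logMAR results as high contrast dim at one week, whereas this trial measures high luminance, high contrast acuity at two weeks. Validity, the non-inferiority conclusion and the sample size, which CLUE vision drives, are unaffected.

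**What to change.** In Section 14.5 and the SAP, name each eye's step 1.14 best-corrected acuity, converted to logMAR, as a fixed covariate in the logMAR mixed model, and state the conversion rule from line and letters read. Say explicitly that step 1.14 is used and not step 1.9, so that the choice is made in advance. Do not use the step 1.24 acuity: it is taken after randomisation with the study lens on the eye, so adjusting for it could remove part of the lens effect.

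The cost is one sentence, a conversion rule and one degree of freedom. No new data, visits or subjects are needed.
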